1.0 BACKGROUND AND RATIONALE

1.1 Background

Parkinson's disease (PD) is a chronic, progressive, neurodegenerative movement disorder characterized clinically by resting tremor, rigidity, bradykinesia and gait disturbance with postural instability. Other features can include masked faces, micrographia, and non-motor features including hyposmia, autonomic dysfunction, mood disturbances, and cognitive dysfunction. Estimates of the incidence and prevalence of PD vary considerably among studies due to differences in study populations, case ascertainment and diagnostic criteria. However, it is recognized that the incidence and prevalence of PD increase with age; and it is estimated that 1–2% of the population aged over 65 years are affected ([Von Campenhausen et al, 2005](#)).

The characteristic pathological findings in the brains of patients with PD are loss of dopaminergic neurons of the substantia nigra pars compacta coupled with the presence of intracytoplasmic inclusions (Lewy bodies). It is now appreciated that neurodegeneration also involves the olfactory system, the cerebral hemispheres, the lower brain stem, the spinal cord, and the peripheral autonomic nervous system. Current therapy is primarily based on a dopamine “replacement” strategy using the dopamine precursor levodopa. Levodopa has revolutionized the therapy of PD, but chronic treatment is associated with the development of motor complications (“wearing-off” and dyskinesia) in the majority of patients. Other available pharmacologic treatments include dopamine agonists, monoamine oxidase type B (MAO-B) inhibitors, and catechol-*O*-methyl transferase (COMT) inhibitors. These have not been shown to be superior to levodopa, but have been shown to either delay the need for levodopa or reduce OFF time in levodopa-treated patients. Each of these agents is thought to act directly on the dopaminergic system. Each has shown benefit, but there remains a need for agents that can treat and prevent motor complications ([Olanow et al, 2009](#)).

Adenosine A2a receptor antagonists have emerged as a potentially attractive new class of drugs for the treatment of PD ([Pinna, 2009](#)). A2a receptors are highly localized in the basal ganglia, specifically within the indirect output pathway which is important in the control of voluntary movement. Alterations in firing patterns in these neurons are also thought to be involved in the development of motor complications induced by levodopa. A2a receptor antagonists modulate gamma-aminobutyric acid and glutamate release in the basal ganglia along with other key neurotransmitters that modulate motor activity. In both rodent and primate models of PD, A2a receptor antagonists have been shown to produce alterations in motor behavior when administered alone or in combination with dopaminergic drugs, suggesting that they might be effective in the symptomatic treatment of PD ([Bibbiani et al, 2003](#); [Yu et al, 2006](#); [Jenner et al, 2009](#)). Because of the potential of A2a antagonists to inhibit abnormal firing of overactive D2-bearing neurons in the indirect striato-nigral pathway, they have the potential to improve OFF time in patients with PD. A2a inhibition may also slow neurodegeneration ([Schwarzschild et al, 2003](#)).

[Redacted text block]

[Redacted text block]

[Redacted text block]

[Redacted text block] nt

[Redacted text block]

[Redacted text block]

[Redacted text block]

[Redacted text block]

[REDACTED]

[REDACTED]

[REDACTED]

[REDACTED]

[REDACTED]

[REDACTED]

[REDACTED]

[REDACTED]

2.0 OBJECTIVES AND ENDPOINTS

2.1 Objectives

2.1.1 Primary Objective

The primary objective of this study is to evaluate the safety and tolerability of tozadenant in levodopa-treated PD patients experiencing motor fluctuations, based on assessment of TEAEs, vital signs, electrocardiograms (ECGs), and clinical laboratory tests.

2.1.2 Secondary Objectives

The secondary objectives of this study are to evaluate the effects of tozadenant on the occurrence of daytime drowsiness, impulsive behavior, and suicidality.

2.2 Endpoints

2.2.1 Safety Endpoints

The safety and tolerability of tozadenant will be evaluated in this study using the following measures:

1. TEAEs.
2. Physical and neurological examination.
3. Supine and standing pulse and BP.
4. Standard 12-lead ECG: RR, PR, QRS, QT and QTcF.
5. Laboratory parameters: hematology, chemistry, thyroid function (thyroid stimulating hormone [TSH], free triiodothyronine [T3], and free thyroxine [T4]), and urinalysis.
6. Daytime sleepiness as measured by the Epworth Sleepiness Scale (ESS), including assessment of episodes of sudden onset of sleep.
7. Modified Minnesota Impulse Disorders Interview (mMIDI).
8. Columbia-Suicide Severity Rating Scale (C-SSRS).

2.2.2 Other Endpoints

The following measures will be assessed to characterize PD status during open-label tozadenant treatment:

- UPDRS Part II (Activity of Daily Living [ADL] subscale) + Part III (motor subscale) total score.

- UPDRS Part II (ADL subscale) score.
- UPDRS Part III (motor subscale) score in the ON state.
- UPDRS Part I total score.
- UPDRS Part IV, including dyskinesia as measured by questions 32, 33 and 34 and motor fluctuations as measured by question 39.
- Clinical Global Impression of Improvement (CGI-I).
- Patient's Global Impression of Improvement (PGI-I).
- Parkinson's Disease Quality of Life Questionnaire 39-Item (PDQ-39; total score and individual domain scores).
- Non-motor Symptom Assessment Scale.
- EuroQol 5D-5L Health Questionnaire (EQ-5D-5L).
- Patient-completed diaries (Change from Baseline in the number of hours per day spent as follows: OFF time, ON time without troublesome dyskinesia, total ON time, ON time with troublesome dyskinesia and asleep time).
- Healthcare Resource Utilization.
- Fall Questionnaire.

3.0 STUDY DESIGN

3.1 Study Description

This is a Phase 3, international, multicenter, open-label study in levodopa-treated patients with PD experiencing end-of-dose "wearing-off". This study includes a Screening Period of up to 6 weeks that starts with a Screening Visit, followed by a 52-week Open-Label Treatment Period and a Safety Follow-Up Visit 4 weeks after completion of investigational treatment. After providing written informed consent, patients will undergo screening evaluations. Patients must meet all inclusion criteria and none of the exclusion criteria and they must successfully complete the diary training and achieve 80% overall diary concordance with the PD diary trainer/rater including at least 1 OFF interval to be considered for randomization. If preliminary eligibility is confirmed by the investigator, patients will then be scheduled for a Baseline Visit and will be required to return a valid set of Baseline diaries. Final eligibility will be determined at the Baseline Visit.

Patients will return to the study site for evaluation at scheduled visits at Weeks 2, 6, 12, 24, 36 and 52. Patients will be contacted by telephone before the start of each 3-day PD diary completion period to be reminded to complete the diary. **Patients will also be scheduled for a laboratory draw (hematology measurement only) at Weeks 4, 8, 10, 16, 20 and 44.** A final Safety Follow-Up Visit (Week 56) will occur 28 ± 3 days after the patient's last open-label dose of tozadenant. Upon starting study treatment, patients will receive open-label tozadenant at a dose of 120 mg BID. Adjustments to the open-label tozadenant dose are allowed to be made by the investigator starting at Week 2 and at any of the subsequent visits. Doses of 60 or 120 mg

BID are permitted; the investigator may adjust a patient's dose to either level as clinically indicated. The Interactive Response System (IXRS) will be used to assign, track and manage the tozadenant inventory at each study site.

Patients' concomitant anti-PD medications may be adjusted as needed under the investigator's supervision (see [Section 5.9.1](#)). The optimal dose of open-label tozadenant for each patient will be defined following discussion between the patient and the investigator, taking into account the potential for improvement of disease symptoms and the tolerability profile.

Unscheduled Visits may be arranged as considered necessary by the investigator (see [Section 6.2.21](#)). In the event of Early Termination, patients will be asked to complete an Early Termination Visit as soon as possible (see [Section 6.2.20](#)) and then return 28 ± 3 days after their last dose of IMP for a Safety Follow-Up Visit ([Section 6.2.19](#)).

Safety data will be provided to the Data and Safety Monitoring Board (DSMB), at a frequency specified by the DSMB charter, for ongoing monitoring of safety and detection of any trends.

3.1.1 Study Duration Per Patient

Each patient will participate for up to 62 weeks, which includes a Screening Period of 1 to ≤ 6 weeks, followed by a Baseline Visit, 52 weeks of open-label treatment, and a Safety Follow-Up Visit 4 weeks after completion of investigational treatment:

- Screening Period: 1 to ≤ 6 weeks.
- Open-Label Treatment Period: 52 weeks.
- Post-Treatment Safety Follow-Up: 4 weeks.

The total anticipated study duration for an individual patient will be a minimum of 57 weeks and a maximum of 62 weeks. The end of the study is defined as the date of the last visit of the last patient in the study.

3.1.2 Planned Number of Patients and Sites

Approximately 645 patients will be screened, assuming a 30% screen failure rate, to enroll 450 patients.

Approximately 120 sites will participate in the study.

3.1.3 Anticipated Regions and Countries

[figure not shown]
This international study will be conducted in North America, Europe, and Asia/Pacific countries.

3.2 Schedule of Events/Evaluations

The Schedule of Events/Evaluations is shown in [Table 1](#) and [Table 1.1](#).

3.3 Schematic Diagram

Figure 1: Schematic Diagram of Study Design

3.4 Rationale for Dose Selection

[REDACTED]

4.0 SELECTION AND WITHDRAWAL OF PATIENTS

4.1 Inclusion Criteria

Patients must fulfill all of the following inclusion criteria in order to be included in the study:

1. Patient is informed and given ample time and opportunity to think about his/her participation in this study and has given his/her written informed consent on an Independent Ethics Committee (IEC) or Institutional Review Board (IRB) approved consent form.
2. Patient is considered reliable and capable of adhering to the protocol (e.g., able to understand and complete diaries), visit schedule, and medication administration instructions according to the judgment of the investigator.
3. Patient has a documented history of idiopathic Parkinson's disease consistent with the UK Parkinson's Disease Society Brain Bank Diagnostic criteria prior to the Screening Visit.
4. Patient has a PD duration of at least 3 years from diagnosis.
5. Patient has a modified Hoehn and Yahr stage 2–4 when in OFF state (estimated) and ≤ 3 in ON state.
6. Patient is male or female and 30–80 years old (inclusive) at Screening.
7. Patient must have a good response to levodopa in the opinion of the investigator, be taking at least four doses of a levodopa-containing medication per day, and at least one other concomitant anti-PD medication (dopamine agonists, MAO-B inhibitors, anticholinergic agents, amantadine or entacapone).
8. Patient is maintained on a regimen of permitted anti-PD medications that has been stable for at least 4 weeks prior to Screening.
9. Patients must have been taking a levodopa-containing anti-PD medication continuously for at least the previous 12 months and must be currently experiencing end-of-dose “wearing-off” with at least 2.5 hours of OFF time per day as confirmed by a 3-day Baseline diary.

10. Patient must have achieved the following results for PD diary training, practice diary collection, and Baseline diary recordings:

- a. During a diary concordance session with an approved PD diary trainer/rater (minimum 2.5 hours), patient achieved at least 80% overall diary concordance including at least 1 OFF interval.
- b. Returned a valid 3-day (i.e., 3 consecutive 24-hour periods) practice diary.
- c. Returned valid diary recordings for each of the 3 consecutive days preceding the Baseline Visit that indicated at least 2.5 hours of OFF time on each of the 3 days.

Note: A valid diary record will not have more than 4 invalid entries (double or missed entries) over a given 24-hour period (defined as starting at 6 AM). An invalid diary entry is defined as more than one entry recorded in a given half-hour interval, an unreadable entry, or the absence of an entry in a given half-hour interval.

Patients will be required to view the PD diary training video. Caregivers may assist patients in completion of the PD diary. If a caregiver participates in completion of the PD diary, he or she is required to participate in the PD diary training session, in addition to viewing the PD diary training video.

Patients who do not meet the criteria for proper practice diary completion may be retrained within the 6-week window of the Screening Period, if the patients are otherwise eligible for the study.

11. Contraception:

- a. Women of childbearing potential must use an acceptable method* of contraception starting 4 weeks prior to study drug administration and for a minimum of 1 month after study completion. Otherwise, women must be postmenopausal (at least 1 year absence of vaginal bleeding or spotting, and confirmed by follicle stimulating hormone [FSH] ≥ 40 mIU/mL [or ≥ 40 IU/L] if less than 2 years postmenopausal) or be surgically sterile.
- b. Men with a potentially fertile partner must have had a vasectomy or be willing to use an acceptable method* of contraception for the duration of the study and for 3 months after study drug discontinuation.

*For men and women: Acceptable methods of contraception include use of a condom with spermicide; oral, implantable or injectable contraceptives; intrauterine device (IUD); diaphragm with spermicide; or, diaphragm with condom. (Note: In Germany, the Czech Republic, and other approved local regions, acceptable methods of contraception include complete abstinence; single barrier [diaphragm or condom] combined with use of IUD or contraceptive [oral, implantable or injectable]; or double barrier [diaphragm with condom]).

4.2 Exclusion Criteria

Patients with any of the following characteristics will be excluded from the study:

1. Patient previously participated in any study with tozadenant.

2. Patient is currently participating in or has participated in another study and received an IMP (active or placebo) or medical device treatment within 5 half-lives of the IMP .
3. Patient has any form of secondary or atypical parkinsonism (e.g., drug-induced, post stroke).
4. Severe obesity defined as a body mass index (BMI) greater than 40.
5. Patient has a QTcF interval of ≥ 500 msec at Screening (Visit 1) or the patient has an average QTcF interval ≥ 450 msec for males or ≥ 470 msec for females at Baseline (Visit 2). The average at Baseline will be taken from 3 serial ECGs done several minutes apart. (Fridericia's correction [QTcF] must be used for correction of the QT interval.)
6. Known diagnosis of malignant melanoma.
7. History of neurosurgical intervention for PD, except for the placement of deep brain stimulator electrodes at least 12 months or greater prior to screening; subjects with deep brain stimulation must not be experiencing any clinically meaningful side effects related to the procedure, the device, or stimulation.
8. Patient with grade 2 hypertension (supine systolic BP ≥ 160 or diastolic BP ≥ 100 mmHg), treated or untreated, at Screening or at Baseline confirmed by at least 1 of 2 further measurements. Patients may be rescreened once if excluded due to this exclusion criterion, following appropriate treatment or treatment adjustment resulting in the resolution of the patient's grade 2 hypertension.
9. Patient with a history of hypertensive crisis unless the underlying cause has been removed (e.g. stenting for renal artery stenosis).
10. Patient has a history of chronic alcohol or drug abuse within the last 2 years.
11. Patient is taking apomorphine, budipine, istradefylline, tolcapone, or [REDACTED], within 4 weeks prior to Screening or is likely to require any of these drugs during the study.
12. Current treatment with antipsychotics; however, quetiapine administered at doses of ≤ 100 mg per day and pimavanserin are permitted if the patient has been on a stable daily dose for at least 4 weeks before Screening. PRN (as needed) dosing is not permitted.
13. Patient has taken digoxin within 4 weeks prior to Screening or is likely to require digoxin during the study.
14. Hyperthyroidism or hypothyroidism, unless all of the following conditions are met:
 - a. Patient has received a stable dose of thyroid medication for at least 3 months before the Baseline Visit.
 - b. TSH concentrations are in the normal range ($\pm 10\%$ as a window either side of the normal range).
 - c. Patient is clinically euthyroid.
15. Any out-of-range laboratory values at Screening that have not been reviewed and documented as not clinically significant by the investigator. Any questionable safety lab results may be repeated for confirmation.

16. A score of < 26 on the Mini-Mental State Examination, Second Edition (MMSE-II) at the Screening Visit. If the MMSE-II is not validated in the requisite language, the MMSE (Original) may be used.
17. Patients with a current episode of major depression. Patients receiving treatment for depression with antidepressants may be enrolled if they have been on a stable daily dose of the antidepressant for at least 8 weeks before the Baseline Visit.
18. Patient has a recent history of suicide attempt (defined as an active, interrupted or aborted attempt within the past 5 years), or reports suicidal ideation in the past 6 months as indicated by a positive response ('Yes') to either Question 4 or Question 5 of the C-SSRS performed at the Screening or Baseline Visit.
19. Patient has evidence of an impulse control disorder (ICD) (i.e., one or more positive modules) according to the Modified Minnesota Impulse Disorders Interview (mMIDI) unless a structured clinical interview performed during Screening confirms that the patient does not have an ICD.
20. Patient is currently lactating or pregnant or planning to become pregnant during the duration of the study.
21. Patient has a known hypersensitivity to any components of the IMP or excipients.
22. Any other condition or clinically significant abnormal findings on the physical or neurological examination, psychiatric and medical history, at Screening or at Baseline that, in the opinion of the investigator, would make the patient unsuitable for the study or put the patient at additional risk or prejudice evaluation of safety and efficacy of the IMP.
23. Patients with alanine transaminase (ALT) or aspartate transaminase (AST) $\geq 3x$ upper limit of normal (ULN), or total bilirubin $\geq 1.5x$ ULN, at Screening.
24. Patients with a history of hepatic dysfunction secondary to viral infection (hepatitis B or C; Epstein Barr virus [EBV]; or cytomegalovirus [CMV]), or a history of diagnosed drug- or alcohol-induced hepatic toxicity or frank hepatitis.
25. Patients with moderate to severe hepatic or renal impairment.
26. 
27. **Patients with absolute neutrophil count less than 2000/mm³ (or 2.0 x 10E9/L) at screening.**

4.3 Criteria for Withdrawal from Study

Patients are free to withdraw from the study at any time, without prejudice to their continued care.

4.3.1 Potential Criteria for Withdrawal from Study

Investigators should contact the Medical Monitor in advance, whenever possible, to discuss the potential discontinuation of a patient from the study. Investigators must contact the Medical Monitor to discuss any of the following events that may lead to the patient being discontinued from the study:

1. Patient is noncompliant with the study procedures or medications.
2. Patient takes prohibited concomitant medications as defined in this protocol.
3. Patient has one or more clinically significant out-of-range laboratory values or clinically significant abnormal findings on physical examination, or AEs that are intolerable (as determined by the patient) or that put the patient at additional risk as judged by the investigator.

4.3.2 Definite Criteria for Withdrawal from Study

Patients must be discontinued from the study if any of the following events occur:

1. Patient develops an illness that would interfere with his or her continued participation.
2. Patient withdraws his or her consent.
3. Confirmation of patient pregnancy during the study, as evidenced by a positive pregnancy test.
4. The Sponsor/Sponsor's designee or a regulatory agency requests withdrawal of the patient.
5. The Sponsor or a regulatory agency terminates the study.
6. Patient has active suicidality since last visit as indicated by a positive response ("Yes") to either Question 4 or Question 5 of the C-SSRS, or reports any suicidal behavior since their last C-SSRS assessment. The patient should be referred immediately to a Mental Healthcare Professional.
7. The patient has a QTcF interval consistently ≥ 500 msec and/or a QTcF interval consistently increased by ≥ 60 msec compared to the average baseline QTcF interval. The average baseline QTcF interval is defined as the average of the three QTcF interval values obtained at Visit 2. Fridericia's method must be used for correction of QT intervals.
8. Investigators must follow guidelines provided related to monitoring hepatic parameters in relation to investigation guidelines and stopping rules. The following necessitate immediate cessation of dosing with IMP:
 - a. Patients with ALT or AST $>8x$ ULN.
 - b. Patients with ALT or AST $\geq 3x$ ULN and co-existing total bilirubin $\geq 2x$ ULN*.
 - c. Patients with ALT or AST $\geq 3x$ ULN who exhibit a temporally associated fatigue, nausea, vomiting, right upper quadrant pain or tenderness, fever (without clear alternative cause), rash or eosinophilia ($>5\%$).

*Patients with significant elevation of alkaline phosphatase (ALP; ALP >2x ULN) indicating biliary obstruction to be discussed with the Medical Monitor.

9. Patients noted to have an elevated BP post-baseline, with a supine systolic BP \geq 160 mmHg and/or a diastolic BP \geq 100 mmHg that is present at 2 consecutive post-baseline study visits.
10. Patients have concomitant surgical intervention for PD, including but not limited to deep brain stimulation.
11. **Patients with an absolute neutrophil count less than 1000/mm³ (or 1.0 x 10E9/L).*** **Following study drug discontinuation, these patients will require weekly hematology measurement until the WBC and/or ANC returns to 75% of the baseline value (Visit 2). Assess for adverse events and concomitant medication changes and record as an unscheduled visit. Discuss with medical monitor to assure that the patient is discontinued from study drug and that the appropriate follow up safety measures are taken.**

*Any patient experiencing a decline in absolute neutrophil count (ANC) and/or white blood cells (WBC) by 50% from baseline (Visit 2) will require weekly hematology measurement until the WBC and/or ANC returns to 75% of the baseline value. The patient will continue with dosing during the weekly hematology follow-up. Assess for adverse events and concomitant medication changes and record as an unscheduled visit. If the WBC and/or ANC returns to 75% of baseline, the patient should return to routine evaluations as outlined in the Schedule of Events/Evaluations. Discuss with medical monitor.

All patients who discontinue prematurely from the study will be requested to return to the study site as soon as possible to complete the safety and efficacy evaluations outlined for an Early Termination Visit in the Schedule of Events/Evaluations (Table 1) and in Section 6.2.20. The Early Termination Visit should be done under IMP treatment, if possible. After Early Termination, the patient will also be asked to return for a Safety Follow-Up Visit to be scheduled 28 (\pm 3) days after their last dose of IMP, unless the Early Termination Visit itself occurred 28 or more days after the last dose of IMP (see Section 6.2.19).

All TEAEs will be followed until resolution, return to Baseline level, or stabilization. Investigators will attempt to obtain information on patients in the case of study withdrawal or discontinuation. For patients considered lost to follow-up, the investigator should make an effort (at least one phone call and one written message to the patient) and document his or her effort (include the date and summary of the phone call(s) and a copy of the written message(s) in the source documents) to complete the final evaluation. All results of these evaluations and observations, together with a narrative description of the reason(s) for removing the patient, must be recorded in the source documents. The electronic case report form (eCRF) must document the primary reason for study withdrawal or discontinuation. Patients who discontinue prematurely from the study will not be replaced.

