Patients who return valid practice PD diaries and who the investigator considers eligible for the study will be scheduled within 6 weeks from the Screening Visit. The patient will be instructed to complete the Baseline PD diary on the 3 consecutive days directly preceding the scheduled Baseline Visit. The trainer/rater will contact the patient prior to the start date to remind them to start keeping the PD diary, to review the ON and OFF definitions, and to answer any questions the patients or caregiver may have regarding completion instructions. The patients will be requested to bring the Baseline PD diary to the Baseline Visit, at which the PD diary will be assessed for validity and to confirm the patient’s eligibility. Patients not meeting the criteria for valid Baseline PD diary completion may be retrained, as described above, and may return for another Baseline assessment within the 6-week Screening Period.

Patients who meet all the entry criteria at Baseline will be assigned IMP using the IXRS and will begin open-label treatment for 52 weeks. The first dose of IMP will be taken at home after the Baseline Visit. Patients will be evaluated at scheduled study visits on Weeks 2, 4, 6, 8, 10, 12, 16, 20, 24, 36, 44, 52, and 56; and will be asked to complete a PD diary on the 3 consecutive days directly preceding visits on Weeks 12, 24 and 52. Prior to each 3-day PD diary completion

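### Weekly hematology can stop on white cell recovery alone, before the neutrophil count that fell has recovered (Protocol 4.3.2)

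*Protocol*

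**What the plan says.** Protocol Section 4.3.2, criterion 11, sets up two streams of weekly hematology.

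- **After withdrawal.** The trigger names one count only: "Patients with an absolute neutrophil count less than 1000/mm³". The drug is stopped and blood is drawn weekly "until the WBC and/or ANC returns to 75% of the baseline value", with Visit 2 as the baseline.
- **On drug (footnote to criterion 11).** The trigger names either count: "Any patient experiencing a decline in absolute neutrophil count (ANC) and/or white blood cells (WBC) by 50% from baseline (Visit 2"). Here "The patient will continue with dosing during the weekly hematology follow-up". The exit uses the same words as above and is repeated in the sentence that releases the patient: "If the WBC and/or ANC returns to 75% of baseline, the patient should return to routine evaluations".

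The and/or exit therefore appears three times. Table 1.1 and Section 6.2.21.1 mention the weekly draws but only refer back to 4.3.2. Neither the protocol nor the SAP says that the count that fell must be the one that recovers.

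**The concern.** An exit joined by and/or is satisfied by either count. After withdrawal for a low ANC, WBC was not the trigger, yet its recovery can end the checks. In the footnote, if both counts halve, the first to recover can end them.

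The protocol treats neutrophils as a specific risk: there is an entry floor (exclusion 27), a mandatory stopping value, and six added hematology-only draws. The footnote patient matters most because exposure continues. Withdrawal at ANC below 1000/mm³ can act only when blood is drawn, so an early return to the routine schedule weakens that safeguard. For the withdrawn patient the stake is smaller: weekly checks may stop before ANC has recovered, but the drug has already been stopped.

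**Working it through.** The plan gives no figure to reproduce. The check is whether WBC can reach 75% of baseline while ANC is still below 75%, and by how much.

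**Inputs from the protocol.** Triggers: ANC below 1000/mm³, or a 50% fall in ANC or WBC (4.3.2). Exit: 75% of the Visit 2 value (4.3.2). Entry floor: ANC 2000/mm³ at screening (4.2). Routine draws follow the "scheduled study visits on Weeks 2, 4, 6, 8, 10, 12, 16, 20, 24, 36, 44, 52, and 56" (6.1).

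**Assumptions not in the documents.** Neutrophil share of baseline WBC, f, from 0.50 to 0.70; other white cells stable.

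**Direction.** Let a be ANC and b the other white cells, each divided by its own baseline. Then WBC/baseline = f·a + (1 − f)·b. Setting this to 0.75, a is below 0.75 exactly when b is above 0.75. WBC therefore gets there before ANC whenever the other cells are above 75% of their baseline at that moment.

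**Size with other cells stable (b = 1).** WBC/baseline = 1 − f(1 − a), which equals 0.75 at a = 1 − 0.25/f.

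| f | WBC/baseline when ANC is at 50% | ANC/baseline when WBC is back at 75% |
|---|---|---|
| 0.50 | 0.750 | 0.500 |
| 0.55 | 0.725 | 0.545 |
| 0.60 | 0.700 | 0.583 |
| 0.65 | 0.675 | 0.615 |
| 0.70 | 0.650 | 0.643 |

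**Withdrawn patient.** Take a Visit 2 ANC of 2000 and a nadir of 900, so a = 0.45. At the nadir WBC is at 0.725, 0.670 and 0.615 of baseline for f = 0.50, 0.60 and 0.70. WBC is back at 75% when ANC = 2000 − 0.25 × 2000/f = 1000, 1167 and 1286/mm³. ANC recovery would need 0.75 × 2000 = 1500/mm³.

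**On-drug patient.** Take a Visit 2 ANC of 3000 that falls 50% to 1500, above the stopping value. WBC is at 75% when ANC = 3000 − 0.25 × 3000/f = 1500, 1750 and 1929/mm³ for the same three shares, against 0.75 × 3000 = 2250/mm³.

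**Can WBC stay at or above 75% throughout?** After an ANC fall of d, it does if f ≤ 0.25/d. That gives 0.50 for d = 0.50, 0.417 for d = 0.60 and 0.333 for d = 0.75; the last two lie below the assumed range of shares.

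**Sensitivity to the other cells.**
- If they rise 20%, with f = 0.60 and a Visit 2 ANC of 3500: baseline WBC is 3500/0.60 = 5833, of which 2333 are other cells. WBC is at 75% (4375) when ANC is 4375 − 1.2 × 2333 = 1575, or 45% of baseline.
- If they fall in the same proportion as ANC, both counts reach 75% together and there is no gap.

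**Gaps after release.** Routine draws are 2 weeks apart to Week 12, 4 weeks apart to Week 24, then 12 weeks (24 to 36), 8 weeks (36 to 44) and 8 weeks (44 to 52).

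**The case against.** The strongest counter-argument is that the footnote's exit mirrors its trigger. Both name either count, and a count can only return if it had dropped, so the natural meaning is whichever count fell. In addition, a footnote patient whose ANC is still at or below half of baseline continues to meet the trigger, so releasing that patient would contradict the same paragraph. Both points have force. They limit the on-drug gap to an ANC between 50% and 75% of baseline and make the footnote ambiguous more than plainly wrong. They do not settle the case where both counts fell, and they do not help the paragraph on withdrawal, where the trigger is ANC alone. With about 120 sites, the ambiguous reading may be applied differently from site to site.

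Second, other safeguards exist. The medical monitor must be consulted, and unscheduled draws are allowed. Clinically significant laboratory findings become adverse events and are followed up, and a blood dyscrasia may qualify as serious. Withdrawn patients have hematology at the Early Termination and Safety Follow-Up visits, subject to the 28-day exception. These are real, and WBC recovery does not end all follow-up. None of them sets an ANC recovery threshold or a weekly frequency.

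Third, the size rests on an assumed neutrophil share and stable other cells, and the 2000/mm³ floor applies at screening while the 75% rule uses Visit 2. That is fair: the figures are illustrations. The direction needs only that the other cells stay above 75% of their baseline.

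**Conclusion.** The concern holds. As written, the exit rule lets WBC end weekly hematology before the neutrophil count has recovered. The mismatch is clearest after withdrawal for ANC below 1000/mm³, where WBC was never the trigger; in the footnote it is an ambiguity that the text does not resolve. With a neutrophil share of 50–70% and stable other cells, release can come at 50–64% of baseline ANC instead of 75%. The gap is wider if other white cells rise and vanishes if they fall in step with ANC. No endpoint, sample size or analysis is affected. The point should be corrected because it concerns a safety rule in a safety trial and part of it applies to patients still taking the drug.

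**What to change.** In all three sentences of Section 4.3.2, end weekly monitoring only when each count that met the trigger (both, if both fell) has returned to at least 75% of its own Visit 2 value. After an ANC below 1000/mm³, always require ANC itself to return to at least 75% of its Visit 2 value, whatever WBC does. Table 1.1 and Section 6.2.21.1 need no change because they refer back to 4.3.2.

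The cost is a protocol amendment to one section and more weekly draws in the patients who trigger monitoring. How many more cannot be worked out from the documents. The 75% threshold is relative, with no absolute ceiling or time limit, so a patient with a high Visit 2 ANC could be followed for longer: a value of 8000/mm³ would require 0.75 × 8000 = 6000/mm³. Whether to add an absolute alternative is a clinical decision for the sponsor and is separate from tying the exit to the right count.
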